## Sample size

- i. Estimated number of participants needed to achieve study objectives and how it was determined, including clinical and statistical assumptions supporting any sample size calculations

We will recruit Veterans until we have reached 100 eligible participants across the three VAMCs. We will randomize eligible Veterans to participate either in the TENACITY intervention (n=50) or enhanced headache usual treatment (EHUT) which may include outpatient clinic-based health psychology (n=50). This is a pilot feasibility demonstration to provide preliminary efficacy. The sample size estimate was based upon the staff resources available to screen, invite and recruit patients to reach 100 subjects over a 15-month period.

## Recruitment

- i. Strategies for achieving adequate participant enrolment to reach target sample size

This study will recruit participants from three geographically distinct VA medical centers. All recruitment procedures will be conducted via phone, with no in-person communication, which will allow for greater reach to include entire VAMC catchment areas and eliminate any potential barriers due to COVID.

Potential participants will be identified by either direct referral from a clinician or from a HCoE-generated recruitment list which utilizes the VHA Headache Data cohort (Sico et al., 2022). The cohort is constructed using VHA electronic clinical and administrative data for Veterans with a headache diagnosis. Research staff will review each Veteran's electronic health record in order to determine if they meet study inclusion criteria. If inclusion criteria are met, the Veteran is sent a recruitment letter by mail which describes patient incentives for participation (\$25) per assessment period and will receive a follow-up phone call. During the phone call, research staff will provide a study overview and conduct further screening if the Veteran indicates interest.

## Methods: Assignment of interventions (for controlled trials)

### Allocation: sequence generation

- i. Method of generating the allocation sequence (eg, computer-generated random numbers), and list of any factors for stratification. To reduce predictability of a random sequence, details of any planned restriction (eg, blocking) should be provided in a separate document that is unavailable to those who enroll participants or assign interventions

We will use a computer-generated random assignment stratified by 3 sites with no blocking.

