## Objectives

The objective of this study is to conduct a pilot randomized controlled trial (RCT) and determine the feasibility of the implementation of a cognitive behavioral therapy (CBT-HA) protocol for headache delivered via telemedicine (TENACITY) compared to enhanced headache usual treatment (EHUT).

The investigators will recruit Veterans diagnosed with chronic migraine during the one-year recruitment period across the 3 VAMCs. The investigators will randomize eligible Veterans to participate either in the TENACITY intervention (n=50) or treatment as usual (n=50).

The specific aims are threefold:

Aim 1: To develop a bundle of evidence-based practice (EBP) implementation strategies to engage 3 VA Medical Centers [2 Headache Centers of Excellence HCoEs and 1 general neurology service] and facilitate their local adaptation and implementation of Cognitive Behavioral Therapy (CBT) (TENACITY) through the vehicle of telehealth services.

Aim 2. To conduct a pilot RCT and determine the preliminary efficacy and feasibility of TENACITY compared to TAU across 3 VA sites. We will conduct a superiority analysis.

Hypothesis 2: Veterans receiving TENACITY will experience a statistically significant reduction in routine clinical headache metrics: headache frequency [headache days per month] (primary outcome), headache-related impairment and psychological symptoms (secondary outcomes) compared to enhanced headache usual treatment at 3 and 6 months.

Aim 3: The investigators will conduct exploratory cost analysis of TENACITY from the Veteran's perspective, using inputs from the pilot RCT, and a two-year budget impact analysis from the VHA's perspective, incorporating the costs of implementation as well as direct costs (and cost-savings,) of providing the TENACITY intervention over all HCoEs to VHA.

Hypothesis 3: TENACITY will be cost-effective and provide value to Veterans and VHA.

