### Interventions: description

The TENACITY intervention consists of protocolled, manualized, short-term cognitive behavioral therapy for headache (CBT-HA) sessions which are administered via a telehealth delivery platform. Each session is approximately 50 minutes and follows a similar structure: (1) agenda setting (2) home practice check-in (3) learning a new skill (4) goal setting for home practice. The treatment will be delivered over approximately six biweekly sessions. (Grinberg et al., 2023)

The enhanced headache usual treatment (EHUT) intervention consists of a referral to behavioral pain therapy contingent on the specific site. The therapies available are cognitive behavioral therapy for chronic pain (CBT-CP), integrated pain mindfulness, and dialectical behavioral therapy. Depending on which format is offered at the specific site, these therapies will be delivered either individually or in a telehealth group setting.

Interventions will be initiated after patient randomization and subsequent scheduling with the appropriate clinician using the VHA clinical scheduler. Treatment will be administered using the VA telehealth platform, VA Video Connect (VVC) and/or telephone in one to one clinical visits.

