## Statistics: outcomes

- i. Statistical methods for analysing primary and secondary outcomes. Reference to where other details of the statistical analysis plan can be found, if not in the protocol

Analyses comparing the TENACITY and EHUT control groups on primary and secondary outcomes will be completed using linear mixed models for hierarchical and longitudinal data (patients are nested within site). The mediating and/or moderating effects of patient-level (e.g., age, gender, and depression) and facility-level variables will be examined.

We will conduct an intention-to treat analysis. A generalized mixed effects model will evaluate the primary outcome of number of headache days and fixed effect of study arm, Visit (time) (Month 3 vs Baseline) and their interaction. Days will be clustered within Veteran and a first order autoregressive structure will be used for the relationship between adjacent days.

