## Statistics: additional analyses

- i. Methods for any additional analyses (eg, subgroup and adjusted analyses)

We will adjust for participant sex.

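### Stratifying by site without blocking is simple randomisation, so neither 50/50 nor balance within site is assured, and the primary model is unclear on site

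*Combined protocol and SAP*

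**What the plan says.** The section on sequence generation states: "We will use a computer-generated random assignment stratified by 3 sites with no blocking". It mentions no minimisation, biased coin or other balancing device.

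Two sections give fixed arm sizes. Sample size says "We will randomize eligible Veterans to participate either in the TENACITY intervention (n=50", with another 50 for the control arm. Objectives says that Veterans will "participate either in the TENACITY intervention (n=50) or treatment as usual (n=50". Neither section gives a target per site.

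Statistics: outcomes treats site in two ways. Its first paragraph covers primary and secondary outcomes and uses "linear mixed models for hierarchical and longitudinal data (patients are nested within site"; it adds that "facility-level variables will be examined". Its second paragraph specifies a generalized mixed model for headache days with "fixed effect of study arm, Visit (time) (Month 3 vs Baseline) and their interaction". Days are clustered within Veteran with a first-order autoregressive structure, and no site term or site level appears. Statistics: additional analyses adds only: "We will adjust for participant sex".

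**The concern.** Stratification balances arms only if assignment is restricted within each stratum, and this plan rules out the usual restriction. Its named stratification factor therefore brings no balance, while the fixed arm sizes read as though the method delivers them.

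Site could plausibly matter here. Study Setting describes three centres with different headache and health psychology services, one of them with no headache psychology program. The control arm's "intervention consists of a referral to behavioral pain therapy contingent on the specific site". A chance excess of one arm at one site would carry that site's average change into the arm comparison. The usual protection is to adjust for site, but the primary model as listed does not, and the general statement can be read either way. Two analysts could fit different primary models and both claim to follow the plan.

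**Working it through.** **Inputs from the documents.** N = 100, 50 per arm (1:1 implied), three sites, no blocking. No alpha, power, effect size, SD or site sizes are given, so there is no sample-size calculation to reproduce.

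**Assumptions.** Site sizes as listed below; site mean changes in headache days of 0/1/2 (mild) or 0/2/4 (strong); residual SD of change 5 or 7 days; two-sided 5% test.

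**1. Equivalence.** If each assignment is an independent 1:1 draw, the TENACITY count at a site of size n is Binomial(n, 0.5). The three counts sum to Binomial(100, 0.5) whatever the site sizes. Convolving the site distributions for 34/33/33, 50/30/20 and 60/30/10 confirmed this.

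**2. Overall split, X ~ Binomial(100, 0.5).**
- P(X = 50) = 0.0796, or 8.0%.
- P(45:55 or worse) = 2 × P(X ≤ 45) = 0.368.
- P(40:60 or worse) = 2 × P(X ≤ 40) = 0.057.

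**3. Cost of the overall split.** Relative efficiency is 4k(100 − k)/100². Its expectation is 1 − 1/100 = 0.99. At 40:60 it is 0.96, so the standard error rises by 1/√0.96 − 1 = 2.1%. A comparison with 80.0% power would fall to Φ(2.802 × √0.96 − 1.96) = 78.4%. The 80% is illustrative, as the plan states no power.

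**4. Split within site.** For n = 33, P(2:1 or worse) = 2 × P(X ≤ 11) = 0.0801. For three such sites, P(at least one) = 1 − (1 − 0.0801)³ = 0.222. By the same rule:

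| Assumed site sizes | P(at least one site 2:1 or worse) |
|---|---|
| 33/33/33 | 22% |
| 34/33/33 | 20% |
| 40/40/20 | 18% |
| 50/30/20 | 21% |
| 60/25/15 | 39% |

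**5. Shift in the arm difference from chance site imbalance.** In 200,000 draws at 34/33/33 the SD was 0.165 days (0/1/2) and 0.331 days (0/2/4). As a check, 2√V/√100 with between-site variance V = 0.667 and 2.667 gives 0.163 and 0.327. Shifts above 0.5 days occurred in 0.3% and 14% of trials.

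**6. Precision lost by omitting site.** The inflation is √(1 + V/SD²) − 1:
- 0/1/2: 1.3% at SD 5 and 0.7% at SD 7.
- 0/2/4: 5.2% at SD 5 and 2.7% at SD 7.

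**7. Simulated mean standard errors.** These come from a linear model of change, 8,000 trials per cell.

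| Site changes, SD | Unrestricted, no site | Unrestricted, site-adjusted | Blocks of 4/6, site-adjusted |
|---|---|---|---|
| 0/1/2, 5 | 1.016 | 1.012 | 0.998 |
| 0/1/2, 7 | 1.417 | 1.421 | 1.395 |
| 0/2/4, 5 | 1.055 | 1.012 | 0.997 |
| 0/2/4, 7 | 1.442 | 1.418 | 1.398 |

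Under unrestricted allocation, omitting site changes the mean standard error by −0.3% to +4.2% relative to adjusting for it, after the degrees of freedom spent. Blocks plus adjustment lie 1.5% to 5.5% below unrestricted and unadjusted. Unadjusted type I error under unrestricted allocation was 4.8% to 5.1%. Blocking without adjustment gave 4.9% and 4.7% (0/1/2) and 3.9% and 4.2% (0/2/4), so it is slightly conservative when sites differ.

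**8. What blocks deliver.** With blocks of 4 and 6, a site's arm difference is at most 3, and at most 2 if its size is even. At 34/33/33 the worst overall difference is 2 + 3 + 3 = 8, or 46:54. In simulation (40,000 draws), 50:50 was exact in about 43% of trials.

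**9. Form of the adjustment.** In a linear model with complete data, a site intercept or a sex main effect moves both visits equally and leaves the arm by visit term unchanged. Only site by visit and sex by visit terms, or an ANCOVA, adjust the change. With a non-linear link this is approximate, and the plan does not state the link.

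**The case against.** The case against concerns weight more than fact. Unrestricted allocation is unbiased, valid and the least predictable scheme, and the plan chooses it openly. Unpredictability has value when one staff member handles randomisation and also conducts participant evaluations. The trial is a pilot sized by staff resources, so no stated power is lost, and 50 per arm reads naturally as a target. Blocks would not make 50:50 certain either. Every site size, site difference and SD above is assumed, and the simulations use a linear model of change, not the planned day-level generalized model. Much of the gain in the strong scenario comes from site adjustment: blocks added to adjustment save only about 1.4% to 1.8% (for example, 0.998 against 1.012). The general statement on nesting may also be meant to govern the primary model. If so, a linear model with a site intercept would give the same primary estimate as one without it.

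Most of this stands, and it limits the severity. It does not remove the point. A stated stratification that has no effect should be made effective or dropped. The text does not say that the first paragraph on modelling governs the second, and the two also differ on linear versus generalized. If they are read together, the trial still gets no effective adjustment of the change for its own stratification factor.

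**Conclusion.** The concern holds. As written, allocation is simple randomisation. This rests on there being no unstated restriction; a fixed per-site list would itself be a restriction and would contradict the text. The plan is also inconsistent on whether the primary model accounts for site.

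The consequence is minor to moderate for a pilot. The estimate is unbiased over randomisation and type I error is about 5%. What is lost is a little precision (size under assumed site effects and SDs only), protection against a chance site imbalance, and a primary model that can be read only one way. The exact probabilities for the overall split need no assumption beyond independent 1:1 draws. The change is worth making because it is nearly free.

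**What to change.** 1. **Allocation.** Use permuted blocks of concealed, randomly varying size (for example 4 and 6) within each site. Alternatively, keep unrestricted allocation, drop the claim of stratification, and describe 50/50 as the expected split.
2. **Analysis.** Reconcile the two paragraphs in Statistics: outcomes and state the link. Then either add site as a fixed effect with site by visit, and sex by visit, to the primary model, or fit an ANCOVA of Month 3 headache days on baseline with site and sex as covariates. A fixed effect is preferable because a random effect is poorly estimated from three sites.
3. **Make both changes together**, since blocking by site while omitting it is slightly conservative. If enrolment has begun, make only the analysis change, before the data are analysed.

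Whether the treatment effect differs by site is a separate question for the planned facility-level moderator analysis.

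The cost is a new list from the same software and one or two sentences of analysis text. The downsides are somewhat more predictable allocation, limited by concealed varying blocks; about 2 to 4 degrees of freedom; and, if sites hardly differ and allocation stays unrestricted, about 0.3% on the standard error.

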### Allocation concealment mechanism

- i. Mechanism of implementing the allocation sequence (eg, central telephone; sequentially numbered, opaque, sealed envelopes), describing any steps to conceal the sequence until interventions are assigned

We will use a password protected computer file to conceal random assignment.

### Allocation: implementation

- i. Who will generate the allocation sequence, who will enroll participants, and who will assign participants to interventions

Program manager will designate the random assignment upon participant completion of the baseline assessment and notify the respective clinical program and schedulers to contact the participants for their respective treatments.

## Blinding (masking)

A TENACITY protocol evaluation will be conducted with participants at approximately 3 months post-treatment initiation in order to evaluate the study arms and exercises used in treatment. To protect research personnel blindness, the research staff member who is responsible for randomization will be the sole staff member to conduct these evaluations and collect self-reported medical care received during the prior 3 months.

## Blinding (masking): emergency unblinding

- i. If blinded, circumstances under which unblinding is permissible, and procedure for revealing a participant's allocated intervention during the trial

## Methods: Data collection, management, and analysis

### Data collection plan

- i. Plans for assessment and collection of outcome, baseline, and other trial data, including any related processes to promote data quality (eg, duplicate measurements, training of assessors) and a description of study instruments (eg, questionnaires, laboratory tests) along with their reliability and validity, if known. Reference to where data collection forms can be found, if not in the protocol

Participants will complete a baseline interview and health questionnaires via phone or electronically using VA Qualtrics. They will be assigned a 31-day headache diary using VA Annie app. Research staff will obtain Veteran permission to audio-record the interviews. Each interview will be recorded and transcribed. The health questionnaires and headache diary will also be completed at 3-month and 6-month post-treatment initiation, along with a treatment satisfaction survey.

At the end of the 31-day run-in period, the participants will be contacted by phone to review the headache diary. If the participant self-reported  $\geq 8$  headache days over the course of the prior 31 days and completed the first question of the headache diary on at least 28 days, s/he will remain eligible for the study. If the participant did not meet these criteria, they will be invited to complete an additional 31 days of headache diary, with the same stipulations applied. If they choose not to complete the headache diary a second time, they will be considered ineligible, removed from the study and sent back to the HCoE clinical provider to review other treatment options. Participants enrolled in the study will then be randomized to either the TENACITY arm or the EHUT control arm of the study.

## Screening Assessments

### *Short Portable Mental Status Questionnaire (SPMSQ)*

The SPMSQ (Pfeiffer, 1975) will be utilized to screen potential participants for cognitive impairment. The SPMSQ is a 10-item measure with scoring guidelines as follows: intact intellectual functioning (0-2), mild intellectual impairment (3-4), moderate intellectual impairment (5-7), and severe intellectual impairment (8-10).

### *American Migraine Study/American Migraine Prevalence and Prevention (AMS/AMPP) Diagnostic Module*

The AMS/AMPP will be utilized to assess Veterans for chronic migraine according to International Classification of Headache Disorders (ICHD-2) criteria. Respondents meet criteria for chronic migraine if at least 2 of 4 pain features are scored as a 3 or more, and nausea or both photophobia and phonophobia are scored 3 or more. The AMS/AMPP has a sensitivity of 91% and specificity of 80% for CM diagnosis. (Lipton, Diamond, Reed, Diamond, & Stewart, 2001)

### *Post-Traumatic Headache (PTH) Screener*

The PTH will be utilized to determine if the participant meets criteria for post-traumatic headache.

### *Patient Health Questionnaire (PHQ-9)*

The PHQ-9 (Kroenke, Spitzer, & Williams, 2001) is a reliable and well-validated self-report measure of depressive symptom severity and suicide risk based on Diagnostic and Statistical Manual of Mental Disorders (DSM) criteria. Items are rated from 0 to 3 (0 = not at all, 3 = nearly every day). Total scores range from 0 to 27. Totals are categorized as follows: none-minimal (0-4), mild (5-9), moderate (10-14), moderately severe (15-19), and severe (20-27). Daily suicidal ideation is indicated by a response of "3" to question nine.

## Primary Outcomes Collection

Reduction of headache days in the 31 days prior to the 3-month post-start of treatment mark is the primary outcome; reduction in headache days in the 30 days prior to the 6-month post-start of treatment mark will allow for measurement of cumulative benefit and persistence of efficacy.

The VA Annie mobile application (Saleem et al., 2020) will be utilized as the platform for a daily headache diary. A protocol has been designed (Table 1) to send daily automated text messages to each participant for a total of 31 consecutive days. Participant responses are stored in the Annie system and are accessible by study staff. If a participant responds that they had a headache, eight additional questions are asked as indicated in Table 1. After being prompted with an Annie question, if the participant does not respond, a reminder message is sent every twenty minutes, with a maximum of three reminders per question.

Q	Text	Response Options	Action
1	Hello, it's Annie. Did you have a headache today?	Yes – HA 2 No – HA 1	If HA 2 → Q2 If HA 1 → Q9
2	On a scale from 0-10, with 0=none and 10=worst, how severe was the headache?	PN 0 – PN 10	If response → Q3
3	Was the pain worse on one side of your head?	Yes – SD 2 No – SD 1	If response → Q4
4	Was the pain pounding/throbbing?	Yes – PD 2 No – PD 1	If response → Q5
5	Did light bother you?	Yes – LT 2 No – LT 1	If response → Q6
6	Did sound bother you?	Yes – SO 2 No – SO 1	If response → Q7
7	Did you feel nauseated or sick to your stomach or vomit?	Yes – VO 2 No – VO 1	If response → Q8
8	Was the pain made worse with routine activities such as walking or climbing stairs?	Yes – MV 2 No – MV 1	If response → Q9
9	On a scale from 0-10, with 0=none and 10=worst, how much did the headache interfere with your life today?	IN 0 – IN 10	

### Secondary Outcomes Collection

#### *Migraine Disability Assessment (MIDAS)*

The MIDAS (Stewart, Lipton, Dowson, & Sawyer, 2001) is a 5-item, self-report measure of disability related to headache based on number of missed or significantly limited activity days due to headache in school or paid work, household work, and family, social, or leisure activities. Responses are categorized as follows: little or no disability (0-5), mild disability (6-10), moderate disability (11-20), and severe disability (21+).

#### *Patient Health Questionnaire (PHQ-9)*

The PHQ-9 (Kroenke et al., 2001) is a reliable and well-validated self-report measure of depressive symptom severity and suicide risk based on Diagnostic and Statistical Manual of Mental Disorders (DSM) criteria. Items are rated from 0 to 3 (0 = not at all, 3 = nearly every day). Total scores range from 0 to 27. Totals are categorized as follows: none-minimal (0-4), mild (5-9), moderate (10-14), moderately severe (15-19), and severe (20-27). Daily suicidal ideation was indicated by a response of “3” to question nine.

#### *Generalized Anxiety Disorder Screener (GAD-7)*

The GAD-7 (Spitzer, Kroenke, Williams, & Löwe, 2006) is a reliable and validated 7-item, self-report measure of anxiety. Items are rated from 0 to 3 (0 = not at all, 3 = nearly every day). Total scores range from 0 to 21 and are categorized as follows: none-minimal (0-4), mild (5-9), moderate (10-14), and severe (15-21) anxious symptoms.

